Funding Type:	 Research Grant  Fellowship  Training Grant  Contract  Other, specify:
Funding Agency:	CDC
Principal Investigator (on proposal):	[name], MPH and [name], Pharm D
Grant Number:	RNG209845
Proposal Title:	Reducing CNS-active Medications to Prevent FALLS and injuries in older adults (STOP-FALLS)
Status:	 New  Competing continuation  Non-competing continuation
Start Date:	9/30/2018
End Date:	9/29/2023
Funded:	 YES  NO
Is the source of this funding federal?	 YES  NO
Is the Department of Defense funding this project?	 YES  NO If YES, contact the IRB staff for guidance.
What institution is the prime recipient of these funds?	University of Washington
If KPWA is the prime recipient, list all institutions that will be sub-recipients of funds on this award:	

2. Study Purpose, Overview, & Background

Guidance: This section of the application provides the IRB reviewer(s) with an overview of the project. Detailed descriptions of study procedures, including recruitment and consent processes, are requested in other sections of the application.

2.1 Objectives

Describe in plain language the purpose, specific aims, or objectives and indicate the primary goal(s) of the study (e.g. safety, tolerability, effectiveness, feasibility, pilot study, etc.). State the hypotheses to be tested. State primary and any secondary study endpoints.

The overall objective of STOP-FALLS is to implement a patient-centered medication reduction program that focuses on CNS-active medications to reduce falls and unintentional injury among older adults. Our aims are as follows: **AIM 1: Adapt and Obtain Feedback on** approaches necessary for adoption and implementation of evidence-based medication reduction strategies (intervention) for use in an integrated health care system. **AIM 2: Implement and Evaluate** the intervention using a cluster randomized trial design. **Aim 3: Assess** barriers and facilitators to intervention adoption, implementation, and maintenance.

2.2 Background

a. Scientific Background

Provide the scientific or scholarly background for, rationale for, and significance of the research based on the existing literature and how will it add to existing knowledge. A short list of references or bibliography must be included as part of this document, uploaded separately, or provide the relevant page number(s) of the grant where references or bibliography can be found.

Falls are a growing public health problem. Falls and fall-related injuries constitute a critical, and growing, public health problem. One in three community-dwelling adults aged 65 and older, and one in two aged 80 and older, sustains a fall each year. About half of all falls result in an injury. Treatment of injurious falls is expensive, costing over \$30 billion annually. As the aging population grows, the adverse impacts of falls (fractures, functional dependency, permanent nursing home residence) will occur with increased frequency, and costs will rise substantially. Systems-based approaches that address the prevention of falls are thus urgently needed. An increased emphasis on fall prevention in clinical practice will greatly enhance the quality of ambulatory care of older adults and stem the rising tide of fall-related healthcare use and costs.

Centrally acting medications are a contributor to falls. Medications, particularly those that affect the central nervous system (CNS), have been consistently linked to falls. Common side effects of CNS-active medications include dizziness, sleepiness, and impaired balance and coordination. Use of CNS-active medications is common, with up to one-quarter of older adults in the community taking at least one of these medications. Importantly, research has found that reduction in these medications can reduce falls. Current practice guidelines recommend that prescribers review all medications with their older patients to minimize polypharmacy and the use of CNS-active and other high-risk medications. However, this practice is not routinely followed due to multiple key barriers: lack of (patient, provider, pharmacist) awareness that medications can cause falls, multiple prescribers, multiple pharmacies, guidelines that induce polypharmacy, patient belief in the need for medication, provider reluctance to change prescriptions, even in the face of patients prompting discussion, and lack of sustainable methods to promote interactions between prescribers, pharmacists, and patients.

b. Benefit to Society

Provide a brief description (a few sentences) of the study's potential benefit to society.

The STOP-FALLS Intervention has the potential to reduce falls and fall-related injuries in adults aged 60 and older using a minimal-risk method. This intervention may also reduce other adverse events including unintentional overdoses and motor vehicle crashes. If it proves to be successful, then this simple intervention could be readily disseminated and at a low cost.

c. Preliminary Data

Provide a brief description of the preliminary data/studies. If there are IRBNet files for those studies, please include the title and number.

Best practices for reducing use of CNS-active medications exist but are underutilized. In preparing this project, we completed a thorough review of the literature and identified two interventions with strong evidence for efficacy in reducing CNS-active medications. We describe these just below.

Eliminating Medications through Patient Ownership of End Results (EMPOWER) is a direct-to-patient educational intervention to reduce use of benzodiazepines in older adults. A randomized trial conducted in partnership with community pharmacies that recruited community-dwelling older adults taking a benzodiazepine found a 27% discontinuation rate at six months. The intervention empowered patients to discuss deprescribing of these medications with their physician or pharmacist but did not engage healthcare providers directly. The investigators found that providers tended to dismiss safety concerns about benzodiazepine use in the context of patient-initiated discussions and believe that this explains why higher discontinuation rates were not achieved ([name], personal communication).

Developing Pharmacist-led Research to Educate and Sensitize Community Residents to the Inappropriate Prescription Burden in the Elderly (D-PRESCRIBE) combined the EMPOWER intervention with a pharmacist-initiated, prescriber-directed, evidence-based decision support tool. This approach achieved a doubling of the six-month discontinuation rate seen with EMPOWER alone.

In summary, evidence suggests that older adults can be educated and empowered to engage in discussions with their providers that result in favorable changes in their medication risk profile (including medications viewed as being difficult to discontinue, i.e., benzodiazepines). Prescriber-directed decision support can also improve the safety of medication regimens. Yet, there remains a need for a pragmatic model that simultaneously engages patients, pharmacists, and prescribers in the context of real-world, daily healthcare delivery to efficiently and safely reduce the use of CNS-active medications. Moreover, models that can sustain prescribing changes over time are paramount to achieve effects on health outcomes such as falls and fall-related injuries, as resumption of medications may otherwise occur.

In STOP-FALLS, we will adapt the EMPOWER patient-directed educational brochure together with the prescriber-directed decision support tool used in D-PRESCRIBE for use within the integrated healthcare delivery system at 9 KPWA clinics. If STOP-FALLS is successful, we expect it to significantly reduce the incidence of falls, fall-related injuries, and healthcare costs for injury care.

d. Data Analysis

Provide a brief description of the main data analysis plan.

Aim 2

Overview. Statistical analyses will be performed using statistical software (R, SAS, or STATA). Descriptive statistics will be computed and appropriate graphical summarizations (histograms, boxplots, scatterplots) will be made for all variables across the intervention clinics and usual care clinics to assess the comparability of the baseline characteristics and follow-up time of each group. Although we stratified our randomization on size and location of clinics and expect the KPWA population to stay relatively stable over the study time period, any patient characteristics which we find to be different (either clinically or statistically at P-value <0.10) between groups at baseline, known to be related to the outcome or likelihood of disenrollment from the health plan will be adjusted for in analyses. We will always include age, sex, and indicator of prior falls in the adjusted models. Statistical significance will be indicated by a P-value <0.05 and all tests and confidence intervals will be two-sided.

Primary Outcome. To compare the primary outcome of reduction in number of medically treated falls between intervention and usual care groups over 12 to 24 months, we will run a Poisson regression model with indicator of intervention or usual care clinic and other adjustment variables. A participant's follow-up time within a clinic will start when they were sent a mailing (intervention group) or comparably for the usual care clinics we will mimic when they would have been sent a mailing if they were in the intervention group and start their follow-up time at that point. To account for differential follow-up time per participant we will include an offset term that is observed follow-up time and accounts for censoring due to disenrollment from the health plan (e.g., offset will be either to the end of the study period between 12-24 months depending on clinic and patient roll-out timing or time enrolled in the health plan over their clinics follow-up periods). To account for cluster randomization at the clinic level we will use generalized estimating equations (GEE) with a robust sandwich variance to account for clinic-level correlation. We will conduct similar models for 6- and 12-month follow-up times which are secondary time points. Further, to explore the timing of when the intervention effect may have occurred, we will run a Poisson model with three indicators of time periods (0-6 months (reference group), 6-12 months, 12-18 months, and 18-24 months) including interactions with time periods and indicator of intervention or usual care clinic. Each participant has up to 4 different outcome measures (less only if censored) in the model and the offset is determined by the time observed in a given time period. To account for multiple outcomes for a participant and cluster randomization we will apply Poisson regression with GEE and a robust sandwich variance.

Secondary Outcomes. To examine the effect of the intervention on unintentional overdose up to 24 months, we will create a binary measure of any healthcare episode for overdose over 24 months. Similar to the analysis of the primary outcome, a Poisson regression model will be used to account for differential follow-up time per participant. We will also examine the effect of the intervention on this outcome every 6 months to explore intermediate trends over time. Motor vehicle crash-induced injuries will also be assessed following the primary outcome analysis. For direct costs of the intervention at 24 months amongst the intervention cohort we will just provide an average cost per patient, standard deviation and range.

Aim 3

Overview. Aim 3 will involve targeted analyses of likely key factors affecting adoption, implementation and maintenance of our intervention. The goal is to generate knowledge that would inform other health systems in their attempts to implement this intervention by obtaining purposely sampled perceptions of delivery system stakeholders (pharmacists, primary care providers, and clinic leadership) of the intervention to inform adoption decisions; describing contextual factors that influence implementation of the intervention; and considering the influence of program costs on intervention maintenance. All data for this aim will be observational (no data collected on patients or providers) to promote feasibility and limit the extent to which self-report measures bias findings, and they will align with established reporting recommendations, wherever possible.

Implementation Strategy Tracking. A published method for tracking strategies will be applied across project meetings to capture information on implementation strategies including: operationalization of each strategy by reporting on the actor of the strategy, the action being performed, the target of the action, temporality, dose, outcome affected, and rationale for strategy selection. We will use structured minute-taking during meetings to capture the information. Strategies will be coded to align with published compilations and reveal novel strategies, consistent with [name] application of this method in an ongoing R01. The richness of the data allows for an understanding of factors affecting implementation, strategies used by whom and how often to achieve what. This information is critical to any form of implementation guide and can allow understanding of any variation in implementation that may be linked to outcomes.

Clinical Leadership. Clinic-level leaders (typically middle managers) are usually the individuals most influential over implementation processes as they are the conduit between high level administrators and front-line providers. Ways in which they shape thinking about and the ultimate form that the STOP-FALLS program takes and how it is integrated into existing workflows will be assessed by ongoing observations of the Implementation Team, with these observations relayed to the research team as part of monthly meetings of the Implementation Team and the research team. Consistent with emerging literature, we will classify the degree to which clinic leaders demonstrate proactive, knowledgeable, supportive, and perseverant leadership for the STOP-FALLS implementation. We will analyze the degree to which these influences helped or hindered intervention adoption and implementation across the KPWA delivery system. We will do this by first classifying clinics as low, moderate, or high performers and then describe leadership characteristics of each clinic group.

Adaptability Analysis. Adaptability of an intervention is important in order to maximize program impact in different settings. We will systematically identify possible adaptations to our intervention and assess whether they might maintain or alter program fidelity, guided by principles of Planned Adaptation. The basic tenet of Planned Adaptation is the imperative to identify core program components, or "elements of a program that fundamentally define its nature and that account for the program's effects", and provide information on potential adaptations of the program (i.e., ways in which the program can be adapted and ways in which it should not be adapted; identifying cultural modifications that do not conflict with the program theory). Adaptations at the clinic level will be tracked by the KPWA Implementation Team, with this information relayed to the research team during joint monthly meetings. We will code adaptations according to an established framework for characterizing adaptations of evidence-based practices post implementation to indicate whether an adaptation was made to the

context, content, or implementation support. We will use adaptation resources (adaptation guidelines, fidelity monitoring tools) to facilitate this process. From this analysis we will make explicit the core components of our intervention and describe ways in which it could be realistically adapted for use in different clinical settings and/or with different patient and provider populations.

Implementation Costs. Contemporaneously, information on direct costs to implement the intervention will be tracked. Costs will be categorized as start-up or maintenance. Start-up costs will include costs to adapt the intervention, time needed to bring the delivery system on-board, staff time needed to identify and invite (mailed letters) eligible patients to participate in the program, overhead (space rental, utilities, supplies), equipment, and personnel costs. Pharmacist time to assess and monitor medication regimens of intervention patients as a result of referrals as well as time to interact with providers will be calculated according to methods used previously. Cost information will be estimated from project invoices, Implementation Team discussions with clinical staff regarding time estimates, and administrative records. We will use descriptive statistics and summarize cost data in terms of a mean intervention cost per patient.

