Eighteen clinics will be randomized to either intervention (n=9 clinics) or usual care (n=9 clinics). Patients meeting the eligibility criteria (see section 3.3) and either assigned to a primary care provider in one of the 9 intervention clinics or receiving primary care in one of the intervention clinics (defined as 1+ visits to the clinic in the year prior to intervention roll-out) are the study intervention group. The study control group will be defined similarly with respect to eligibility criteria and assignment/visits to the usual care clinics. The sample is static (identified once at the time of study roll-out at the particular intervention clinic and matched usual care clinic) throughout the study.

The intervention will be rolled out at a rate of 1-3 clinics each month (tentative start date of July 2020) and the intervention will persist in each clinic for up to 12 months (see Table in Section 2.3.c for roll-out schedule).

In order to ensure that KP providers are not confused by this communication, we will inform providers at the 9 Intervention Clinics about this study and materials that they can expect to receive (via Epic Staff Messaging) by attending morning huddles and/or brown bag lunches as deemed appropriate by the clinic managers. During the intervention period, intervention

group participants (and their providers) will receive brochure(s) specific to the medication class or classes they are currently taking. A maximum of approximately 35-95 intervention participants per clinic will receive mailings each month for opioids, z-drugs, skeletal muscle relaxers, TCA, and prescription antihistamine users. We refer to this herein as our “max cap” per clinic each month (this number represents ~15% of monthly clinic visits by the intervention sample and has been agreed upon with by the KPWA delivery system). The maximum number has a range because it will vary by clinic according to total eligible patient participants and the expected number of patient visits per month. For the mailing of antihistamine brochures to all participants, except those who already received one because they were identified as prescription antihistamine users, the max cap will not apply. We will mail the antihistamine brochure once to all eligible patients who have not already received an antihistamine brochure due to a chronic (>3 months) antihistamine prescription.

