KPWA VDW	All healthcare utilization such as primary care visits, specialty visits, emergency department visits, inpatient stays, nursing homes, etc.	6/1/2019 – 6/30/2022
KPWA VDW	Pharmacy dispensing data on all medications (drug name, date of dispensing, strength, quantity, days supply, provider id, NDC)	6/1/2019 – 6/30/2022
KPWA VDW	Demographics (e.g., age, sex, race)	6/1/2019 – 6/30/2022
KPWA Clarity	Patient reported outcome scores and dates questionnaire was administered – pain (PEG), anxiety (GAD), depression (PHQ-9), insomnia (ISI)	6/1/2019 – 6/30/2022
KPWA clinical notes in the EMR (extracted with natural language processing)	Mention of symptoms (yes, no) or scores for symptom questionnaires on pain, anxiety, depression, and insomnia. Date of mention or administration of questionnaire.	6/1/2019 – 6/30/2022
KPWA EMR	Date and provider of scheduled PC visits	6/1/2019 – 6/30/2022
KPWA EMR	Referrals to pharmacy (y, n) and date	6/1/2019 – 6/30/2022
KPWA VDW	Provider ID, Specialty, Provider Type, primary practice clinic. Data collected so that we can determine who the patients' PCP is for faxing the EBPO to the correct provider).	Intervention Launch to Intervention End

Waiver of Consent/HIPAA Authorization Protocol (December 2020-)

Data from KP Washington or KPWHRI Study		
Source (specify) (i.e., from KPWA, or an existing or previous study, etc.)	Key Information/Description of Variables	Date Range
KPWA VDW	
Diagnosis codes:
 
For outcomes including:
 
 • Injury diagnostic codes • Fall-related diagnostic codes • Motor vehicle crash (MVC)-related diagnostic codes • Unintentional overdose-related diagnostic codes • Adverse drug withdrawal event (ADWE) diagnostic codes 
For chronic conditions associated with falls, e.g.:
 
arthritis, back pain, knee pain, alcohol use disorder, chronic lung disease, congestive heart failure, diabetes, heart disease, hip fracture, hypertension, obesity, peripheral neuropathy, osteoporosis, Parkinson's disease, stroke, urinary incontinence, impaired vision, impaired hearing, memory problems, non-melanoma cancers, frailty
 
For other diagnoses related to medication prescription for the following conditions:
 
anxiety, depression, insomnia, chronic pain
	6/1/2019 – 9/30/2024

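### Primary-model covariates beyond age, sex and prior falls are chosen by baseline differences (P<0.10 or an undefined clinical difference) and are not fixed before outcomes are extracted

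*Combined protocol and SAP*

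**What the plan says.** The rule is in the Aim 2 overview of section 2.2.d. The analysis will adjust for "any patient characteristics which we find to be different (either clinically or statistically at P-value <0.10) between groups at baseline", and the sentence goes on: "known to be related to the outcome or likelihood of disenrollment from the health plan will be adjusted for in analyses". Three covariates are fixed: "We will always include age, sex, and indicator of prior falls in the adjusted models".

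The primary-outcome paragraph adds no further names: "we will run a Poisson regression model with indicator of intervention or usual care clinic and other adjustment variables". For the outcome model, clustering is handled explicitly: "we will use generalized estimating equations (GEE) with a robust sandwich variance to account for clinic-level correlation". No equivalent is stated for the baseline comparisons.

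The documents do not give a closed list of candidate covariates, a definition of a clinical difference, the baseline test to be used, or a date by which the list is fixed. The nearest thing to a candidate pool is the diagnosis row in section 7.3.d (waiver-of-consent table). It lists fall-associated conditions ("arthritis, back pain, knee pain, alcohol use disorder, chronic lung disease, congestive heart failure, diabetes" and others) and has the same extraction window as the outcome codes, 6/1/2019 to 9/30/2024.

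**The concern.** When clinics are randomised, baseline differences between arms arise by chance, so a baseline P-value tests something already known. What makes a covariate worth adjusting for is how strongly it predicts falls. A significance screen can admit weak predictors that happen to differ and pass over strong ones that happen to be balanced.

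The qualifying phrase does not settle this, because the grammar allows two readings:

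- **As a restriction.** A variable must differ at baseline and also be related to falls or disenrollment. Strong predictors that are balanced are then left out.
- **As a separate route.** Known predictors enter whether or not they differ. The P<0.10 test then adds only variables not known to matter.

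Neither reading gives the significance test a useful job, and the two lead to different primary models. The clinical-difference criterion, judged on data already in hand, leaves further discretion. At stake is whether the primary analysis can be written down in full before anyone sees falls by arm.

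**Working it through.** The plan gives no power, event rate or ICC, so there is no figure of its own to reproduce. The check asks how many covariates the rule would admit by chance.

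**Inputs**
- About 5,000 patients (section 3.1) in 18 clinics, nine per arm (sections 7.1.a and 7.1.e): m = 5000/18 = 277.8 per clinic.
- Screening level 0.10, two-sided (section 2.2.d).
- Candidates: 21 fall-associated conditions plus 4 prescribing-related diagnoses in section 7.3.d, 25 in all. Treating these as the candidate pool, and as independent, is an assumption.
- ICC of a baseline covariate: not in the documents; assumed 0 to 0.05.

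**1. Test that respects clustering.** The flag rate is 10% at any sample size (simulated 9.6% to 10.6%). Expected flags = 25 × 0.10 = 2.5. P(at least one) = 1 − 0.90^25 = 92.8%. P(at least five) = 9.8%.

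**2. Patient-level test that ignores clustering.** DE = 1 + (277.8 − 1) × ICC, and flag rate = 2[1 − Φ(1.645/√DE)]. The simulated rates use 4,000 runs per ICC. The last column adds the three fixed covariates, treatment and intercept, at one parameter each.

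| ICC | DE | Flag rate | Simulated | Flags of 25 | Parameters |
|---|---|---|---|---|---|
| 0 | 1.00 | 10.0% | 9.8% | 2.5 | 7.5 |
| 0.01 | 3.77 | 39.7% | 39.8% | 9.9 | 14.9 |
| 0.02 | 6.54 | 52.0% | 52.7% | 13.0 | 18.0 |
| 0.05 | 14.84 | 66.9% | 66.6% | 16.7 | 21.7 |

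The middle matrix of the sandwich variance is built from 18 clinic contributions, so its rank is at most 18. The rule sets no limit that keeps the parameter count well below that.

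**3. Size of difference that triggers entry.** For a patient-level test this is 1.645 × √(4/5000) = 0.047 SD. For a clinic-level t test on 16 df it is 1.746 × √(4 × DE/5000), which gives 0.096 SD at ICC 0.01 and 0.190 SD at ICC 0.05. The unstated choice of test therefore moves the entry threshold up to fourfold (0.190/0.047).

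**4. Effect on the primary test.** Two simulations with no treatment effect used 18 clinics of 278 patients, 21 candidates and covariate ICCs of 0.01 to 0.05.
- Weakly prognostic binary candidates, with assumed fall rate and clinic variation, 800 runs per ICC. Type I error was 6% to 9% both with selection and with the three fixed covariates alone, so the excess over 5% is not due to selection. The significance verdict differed between the two models in 1.4%, 2.1% and 4.5% of trials at ICC 0.01, 0.02 and 0.05.
- Linear outcome, outcome ICC 0.01, coefficient 0.1 per candidate, t reference on 16 df, 1,200 runs per ICC. Type I error with selection was 4.5%, 3.9% and 4.2%. The SD of the estimate was 0.056, 0.055 and 0.057, against 0.055, 0.054 and 0.056 when all 21 were always included. That is a loss of about 2%.

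**The case against.** The strongest defence is that the plan does not ignore prognosis. The sentence names relation to outcome and to disenrollment, three sensible covariates are always in, and the model form, offset and clinic-level GEE are stated. Selection looks at baseline data, not falls. With nine clinics per arm, chance imbalance can be appreciable, and wanting to adjust for it is reasonable. Section 7.3.d is a data-collection table that no text calls the adjustment list, and most of its conditions are labelled as fall-associated, so flagging them would not bring in irrelevant variables. Section 2.2.d also answers a form prompt for a brief description.

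Much of this stands, and it rules out four stronger readings that a reader might infer:

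- **That 5,000 patients by themselves make the screen flag many covariates.** A valid test flags 10% at any sample size. The 40% to 67% figures need a test that ignores clustering, and the documents do not say which test is meant.
- **That the primary model is unknown.** Its core is specified; only the further covariates are open.
- **That covariates are chosen on outcomes.** The text does not say so. It only fails to commit to fixing the list first.
- **That the error rate is uncontrolled.** Neither simulation showed inflation from mechanical selection, even where about 14 of 21 candidates would be flagged.

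What does not stand is that the qualifying phrase rescues the rule. Its ambiguity is part of the problem. Nor does brevity excuse it, because a significance screen is stated and a better rule would take no more space. Adjusting for named prognostic factors deals with the imbalances that matter; a sensitivity analysis can address the rest.

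**Conclusion.** The concern holds in a limited form. A baseline difference at P<0.10, or an undefined clinical difference, is a stated route into the primary model. The covariates beyond age, sex and prior falls are not fixed, and nothing commits to fixing them before outcome extraction.

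If the 25 diagnoses are the candidates and are independent, chance selection of at least one is likely (93%) even with valid tests. With tests that ignore clustering, about 10 to 17 would be flagged at ICC 0.01 to 0.05, which brings the parameter count close to or past the 18 clinics. These counts are illustrative. Under the separate-route reading, known fall predictors would enter untested, and the counts would apply only to whatever else is screened.

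The consequence is an incompletely specified primary analysis with room for discretion, and possibly a small loss of precision (about 2% in one simulated setting). It is not demonstrated type I error inflation. The discretion has some practical weight: with and without the flagged covariates, significance differed in 1.4% to 4.5% of simulated null trials.

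**What to change.** In section 2.2.d, delete both the P<0.10 and the clinical-difference criteria. Before outcomes are extracted, date and fix a short primary covariate list:

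- age, sex and prior falls, as now;
- target medication class at roll-out;
- a few named fall-related conditions from section 7.3.d, chosen on prognosis;
- optionally, the stratification factors of clinic size and location (section 7.1.a) in low-parameter form.

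Keep the total number of parameters small relative to 18 clinics. State that this adjusted model is the primary one. Report baseline balance descriptively, for example as standardised differences, without tests. Keep the minimally adjusted model and any imbalance-driven adjustment as labelled sensitivity analyses.

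The cost is SAP wording and a little more analysis work. The suggested covariates draw on data the plan already intends to collect.
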